13 ESTABLISHMENT OF REGISTRY FOR SUBJECT FOLLOW-UP – VTL-308E

VTL intends to provide for long-term follow-up of subjects recruited into this trial through establishment of a registry which is described in the extension protocol VTL-308E.

13.1 VTL-308E JUSTIFICATION

VTL is conducting clinical trial VTL-308, in which subjects with AILD are treated with ELAD and standard of care, or with standard of care alone to assess the safety and efficacy of ELAD treatment.

A hypothetical risk exists that over an extended period of follow up there may be an increased incidence of tumor formation in subjects treated with ELAD. However, the underlying disease processes in subjects with alcoholic hepatitis also leads to an increased risk of tumor formation in the liver and elsewhere. Worldwide, hepatocellular cancer is the fifth most common cancer in men and eighth most common cancer in women, varying in accordance to prevalence of hepatitis B and C infections, and well over 80% of all primary liver cancers are caused by chronic hepatitis infections ([Bosch and Diaz 2004](#)).

The VTL-308 trial monitors subject safety up to 91 days after Randomization. To assess whether there is an increased risk of late tumor formation in subjects treated with ELAD, this registry protocol segment of VTL-308 extends the safety monitoring period to 5 years.

VTL-308E is designed to provide a long-term assessment of subject's outcome in relationship to tumor (in particular liver tumor), liver transplant, and overall mortality. The protocol includes both control and ELAD-treated subjects to assess the significance of any findings.

13.2 OBJECTIVES

The intent of this protocol is to determine the status of VTL-308 study subjects at 6 months (± 2 weeks), 9 months (± 2 weeks), 1 year (± 2 weeks), and then annually for 4 additional years (± 2 months) following their participation in the study to assess:

- Survival
- Incidence and characterization of tumor (in particular hepatocellular tumor)
- Incidence of liver transplant
- Quality of life using a standard, validated questionnaire

Subjects who withdraw prior to Study Day 91 and who continue to consent to be followed in the VTL-308E study will be contacted according to the VTL-308E procedures at each of the remaining parent study scheduled visits (e.g. Study Day 28, Study Day 63, Study Day 91). VTL may request additional unscheduled contacts during the extension period in order to support survival analyses, particularly around the time of completing the parent study.

13.3 SUBJECT POPULATION

Since this is a follow-up segment to the VTL-308 study, only subjects participating in VTL-308 will be considered for enrollment into this protocol. Subjects lost to follow-up in VTL-308 will be considered as the same, lost to follow-up, for this extension segment of this protocol (VTL-308E).

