7 STATISTICS AND METHODS OF DATA ANALYSIS

7.1 SAMPLE SIZE RATIONALE

The sample size is based on experience from the VTI-208 study.

Analysis of the VTI-208 data suggests that in a group of subjects meeting the inclusion criteria for VTL-308 it might be reasonably anticipated that the hazard rate in the control group will be 0.004 and the hazard ratio 0.4 in favor of the ELAD group. Under the assumption of a proportional hazards model, this leads to median survival estimates of approximately 175 days and 438 days for Control and ELAD subjects, respectively.

The VTL-308 inclusion criteria have been established to reflect the same study population as that enrolled in a subset of the VTI-208 population with baseline criteria including MELD <30, age <50, INR \leq 2.5, creatinine <1.3 and serum total bilirubin \geq 16mg/dL, to define the ITT population, with key safety criteria also applied prior to initiation of ELAD treatment and at End of Study Day 2 (EOSD 2) in the Control group to establish the mITT population. Applying these criteria to the analysis of the primary endpoint of overall survival in the ITT population, and assuming: 1) that this prospectively-defined population behaves similarly to this subgroup of the VTI-208 study; 2) the use of a log-rank test comparing two survival curves with a two-sided significance level of 0.05; 3) exponential survival curves with proportional hazards; 4) uniform accrual with an accrual time of at least 720 days and a minimum follow-up time of 90 days; and 5) a drop-out rate of 10%, a sample size for VTL-308 of 75 subjects per group with 1:1 allocation is consistent with power of at least 0.95 with estimated median survival times of 175 and 438 days respectively.

Due to the distribution of subjects between the ITT and mITT group it may be necessary to enroll more than 150 subjects total in order to ensure that there are a minimum of 75 subjects actually treated with ELAD in the ITT population. Consequently, enrollment may continue until ELAD treatment has been initiated on 75 subjects.

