If the contact person cannot be reached by phone (at least 3 attempts), a registered letter will be sent to both the study subject and to the contact person requesting contact information for them both.

If no information is forthcoming within 3 weeks of sending the registered letters, the subject will be considered lost to follow-up. No further attempts will be made to reach the subject or the contact person. VTL should be notified of the lost-to-follow-up status by calling the office at [contact] and asking for any of the VTL-308 staff.

If at a later time, the subject or the contact person responds, the study visit should be done at that time, even if it is late. The protocol will resume on the following anniversary, so ensure that VTL is made aware of the late contact to keep the subject on the call reminder list.

The site should look in their medical records for any information regarding possible death of the subject if they get no response to calls. All deaths will be noted on the eCRF.

Prior to calling a subject annually, the previous year's information will be reviewed to assure no subject contact is inadvertently made if the subject has expired and we have been made aware of it.

For subjects lost to follow-up, whether during or after the 91-day parent study, VTL may engage a third party vendor that specializes in identifying survival status (e.g. through a search of public records). In such cases, this vendor will provide documentation of the survival status to study site, who will then enter this new information in the eCRF.

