1.3 SAMPLE SIZE RATIONALE

The sample size is based on experience from the VTI-208 study.

The VTL-308 inclusion criteria have been established to reflect a subset of the VTI-208 population, i.e. the VTI-208 population with baseline criteria of MELD <30, age <50, INR \leq 2.5, creatinine <1.3 mg/dL and serum total bilirubin \geq 16 mg/dL.

The key design feature of the VTL-308 Protocol is that the primary analysis of treatment effect on overall survival is based on a log-rank statistic having two-sided significance level of 0.05. This primary analysis will be performed when the last of 150 randomized subjects has been followed for at least 91 days. Sample size adjustments may be made only in the instance in which more than 150 randomized subjects would be needed in order to achieve the minimum threshold of 55 deaths at the time of that analysis.

When the study is nearing completion of enrollment, the total number of deaths occurring through that time will be calculated, along with the mortality rate, based on the enrollment rate per month and the time to death. Based on these calculations a projection will be made of the total number of subjects that will need to be enrolled to achieve the minimum threshold of 55 deaths at the time of study data lock (estimated to be approximately 5 months after last patient enrolled). The total sample size may then be adjusted accordingly.

Analysis of the VTI-208 data suggests that in a group of subjects meeting the inclusion criteria for VTL-308, it might be reasonably anticipated that one-year survival will be in the range from 40% to 48% in the Control group. Under the assumption of a proportional hazards model, if the hazard ratio is 0.4 in favor of the ELAD group, this leads to the anticipation that one-year survival will be in the range from 69.5% to 74.5% in the ELAD subjects.

The rationale for the sample size is based on the following assumptions:

- the analysis of the primary endpoint of overall survival will be conducted in the ITT population;
- the prospectively defined population behaves similarly to the corresponding subgroup of the VTI-208 study;
- the log-rank test will be used to compare two survival curves using a two-sided significance level of 0.05;
- one-year survival will be in the range from 40% to 48% in the Control group and in the range from 69.5% to 74.5% in the ELAD group;
- the accrual distribution will be uniform with an accrual time that will be at least 720 days;

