- the rate of missing data will be in the range from 0% to 10%; and
- the primary analysis will be the time when at least 55 deaths have occurred and the time when the last enrolled subject has been followed for at least 91 days. It follows that a sample size for the VTL-308 trial of 75 subjects per group with 1:1 allocation would provide a number of events (i.e., deaths) in the range from 55 to 65, even if we assume average follow-up of only 1 year. With 55 events, the trial will have 90% power if the true hazard ratio is 0.417; with 65 events, the trial will have 90% power if the true hazard ratio is 0.447.

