7 EFFICACY ANALYSIS

Unless otherwise specified, all analyses will be of randomized subjects by treatment group.

No data imputation will be used, except for the ECBL and Lille analyses. For the primary log-rank analyses of the effect of ELAD on OS, the subject's last available study evaluation through Day 91 after the calendar date at which the last subject was randomized will be used. This OS follow-up will draw from data generated by VTL-308 and VTL-308E follow-up data. Every effort will be made to capture the survival status of each randomized subject through Day 91 after the calendar date at which the last subject was randomized.

For the log-rank analysis of the effect of ELAD on OS, the null hypothesis will be that the true survival curves do not differ and will be tested at the two-sided 0.05 level of significance. The primary efficacy analysis will be carried out on the ITT population, and sensitivity analyses will be performed using the mITT, PP and Safety populations. Kaplan-Meier estimates of survival will be generated for both treatment groups, and estimates will be obtained for median survival, 25th and 75th quartiles. A Cox regression analysis will be performed to obtain an estimate of the hazard ratio and corresponding confidence limits. Exploratory analyses of treatment effect within subgroups will be performed.

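### Whether deaths after loss to follow-up enter the primary survival test is left to an optional vendor search, decided by a sponsor who can see allocation

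*Protocol*

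**What the plan says.** Survival beyond Day 91 in the primary analysis comes from the extension, VTL-308E, through a snapshot taken at the VTL-308 database lock (SAP 5). These provisions decide what happens to a subject who is lost.

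- Protocol 13.3: "Subjects lost to follow-up in VTL-308 will be considered as the same, lost to follow-up, for this extension segment".
- Protocol 13.4, once calls and registered letters have failed: "No further attempts will be made to reach the subject or the contact person".
- Protocol 13.4, last paragraph: "For subjects lost to follow-up, whether during or after the 91-day parent study, VTL may engage a third party vendor" that identifies survival status, for example from public records. The vendor documents the result to the site, which enters it in the eCRF.
- Protocol 5.5.8 and 13.4 accept survival information that arrives late and ask sites to check their own medical records for a possible death.
- SAP 7: "Every effort will be made to capture the survival status of each randomized subject through Day 91 after the calendar date" on which the last subject was randomized. SAP 7.1.1 accepts that some subjects may still be lost and censors them when their status was last known.
- SAP 7.2.1: the first-listed Day 28/91 analysis keeps anyone not known to be dead in both numerator and denominator. An additional analysis leaves out subjects of unknown status.
- Protocol 5.3.2: each assignment is available to the site and the sponsor in the EDC system and is sent to the designated sponsor team by e-mail.

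**The concern.** Section 13.3 and the last paragraph of 13.4 do not fit together on survival status. The first carries the lost status into the extension. The second allows the same subjects to be traced, but only if the sponsor so chooses. No trigger, date, scope or both-arm rule is given. The SAP's censoring rule does not fill the gap, because the date on which status was last known itself depends on whether a search was run.

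The trial is open-label and the party holding the option can see allocation. A death after loss counts as an event if the search is run and otherwise may appear only as a censored observation. In the first-listed Day 28/91 analysis, an untraced subject who died before the time point counts as a survivor. Search timing can also affect the death count that SAP 1.3 uses near the end of enrollment to decide whether to enlarge the sample. A choice of this kind in a pivotal trial should be fixed in advance, even if nobody intends to misuse it.

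**Working it through.** **1. The plan's own power figures.** The test is stated as "the log-rank test will be used to compare two survival curves using a two-sided significance level of 0.05". With d deaths and 1:1 allocation, Schoenfeld power is Φ(|ln HR|·√d/2 − 1.96).

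- d = 55, HR 0.417: 0.8747 × 3.7081 − 1.96 = 1.283, power 0.900. SAP 1.3 says "With 55 events, the trial will have 90% power if the true hazard ratio is 0.417".
- d = 65, HR 0.447: 0.8052 × 4.0311 − 1.96 = 1.286, power 0.901. SAP 1.3 says "with 65 events, the trial will have 90% power if the true hazard ratio is 0.447".

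Both reproduce.

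**2. How many deaths are at issue.** Inputs from the documents:

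- 75 per arm, uniform accrual over 720 days and follow-up to Day 91 after the last randomization, so follow-up C is uniform on 91 to 811 days.
- Protocol 7.1: "the hazard rate in the control group will be 0.004 and the hazard ratio 0.4 in favor of the ELAD group", that is λ = 0.004 and 0.0016 per day.
- SAP 1.3 mid-range one-year survival of 44% and 72%: λ = −ln 0.44/365 = 0.00225 and −ln 0.72/365 = 0.00090.
- Loss: 10% drop-out (Protocol 7.1, timing not stated); 0-10% missing (SAP 1.3).

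Assumptions of this check: exponential survival, an unchanged hazard after loss, and two patterns for the timing of loss.

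- Alive at cut-off: S = (e^(−91λ) − e^(−811λ))/(720λ).
- Alive at loss, loss uniform over Days 0-91: A = (1 − e^(−91λ))/(91λ).
- Alive at loss, loss uniform over the subject's own follow-up: B = mean over C of (1 − e^(−λC))/(λC).
- Deaths after loss, with a fraction p lost: 75p × the sum over arms of (A − S) or (B − S).

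Values (control, ELAD):

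- Protocol hazards: S = 0.228, 0.513; A = 0.838, 0.931; B = 0.497, 0.723. Expected deaths 75 × (0.772 + 0.487) = 94.4. At 10%: early loss 7.5 × (0.610 + 0.417) = 7.7; spread loss 7.5 × (0.269 + 0.210) = 3.6.
- SAP mid-range: S = 0.404, 0.678; A = 0.904, 0.960; B = 0.646, 0.826. Expected deaths 75 × (0.596 + 0.322) = 68.9. At 10%: early loss 7.5 × (0.501 + 0.282) = 5.9; spread loss 7.5 × (0.242 + 0.148) = 2.9.

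| Deaths after loss | Expected deaths | 10%, all by Day 91 | 10%, spread | 5%, all by Day 91 | 5%, spread |
|---|---|---|---|---|---|
| Protocol hazards | 94 | 7.7 | 3.6 | 3.9 | 1.8 |
| SAP mid-range | 69 | 5.9 | 2.9 | 2.9 | 1.5 |

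**3. What discretion does to the test.** The log-rank test was simulated with 75 per arm, hazard 0.004 per day in both arms (no effect), 720-day accrual, 90-day minimum follow-up and all losses before Day 91, 10,000 runs each. The entries are one-sided error in favour of ELAD (nominal 0.025, Monte Carlo error about 0.002).

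| Rule | 5% lost, hazard unchanged | 10% lost, hazard unchanged | 10% lost, hazard doubled after loss |
|---|---|---|---|
| No search | 0.0248 | 0.0260 | 0.0283 |
| Search all, both arms | 0.0244 | 0.0249 | 0.0287 |
| More favourable of these two, chosen after results | 0.0296 | 0.0332 | 0.0345 |
| Control arm only, deaths and survivors updated | 0.0236 | 0.0254 | 0.0483 |
| Control arm only, deaths added | 0.0288 | 0.0384 | 0.0533 |

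Mean deaths after loss were 4.6, 9.1 and 11.0 in the three columns. With 10% lost and an unchanged hazard, searching all and searching none disagreed on two-sided significance in 2.9% of null trials and in 7.7% of trials at HR 0.6.

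**4. What one fixed rule does.** With 10% lost, searching everyone in both arms gives two-sided error of 0.050 (unchanged hazard) and 0.053 (doubled). Power at HR 0.6 is 0.735, against 0.703 with no search. At HR 0.4 the two rules hardly differ (0.991 and 0.989).

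**The case against.** The other side has a good case on several points.

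- A reader might infer that the SAP guarantees survival status for everyone and so contradicts the protocol. It does not. It commits to best effort, expects some loss and gives a censoring rule.
- A reader might infer that 13.3 stops survival data at the last contact. It assigns a status and does not bar recording a death. Protocol 5.5.8 and 13.4 admit late information and ask for record checks, and 13.4 puts a subject who responds late back on the schedule.
- Within 13.4, the sentence ending further attempts concerns reaching the subject or the contact person. A public-records search is not such an attempt, so these two sentences can stand together.
- Selective searching is not stated. The vendor paragraph addresses lost subjects as a class, and results go through the site.
- The 6 to 8 deaths are an upper end. They use the top of the SAP's missing-data range, put every loss before Day 91 although weekly home visits after discharge run to that day, and allow no recovery by the other routes. They arise where 69 to 94 deaths are expected, so setting them against the 55-death floor exaggerates them.
- That loss goes with relapse and death is plausible, but the documents do not say so.

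All of this stands and limits the point. None of it supplies the missing rule. Late information and record checks are passive or depend on the site, and the clause in SAP 1.1 that lets the SAP override the protocol has no vendor-search rule to apply.

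**Conclusion.** The concern holds in a limited form. Sections 13.3 and 13.4 need to be reconciled, and an ascertainment step that feeds the primary endpoint is left to a sponsor with access to allocation. About 1.5 to 7.7 deaths are at issue, of 69 to 94 expected, assuming 5-10% lost and an unchanged hazard after loss. With no loss the issue disappears.

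The error rates belong to the upper end, with 10% lost before Day 91. An all-or-none choice made after seeing results gives about 0.033 instead of 0.025 one-sided, which is modest. Adding only control deaths gives 0.038, or 0.053 if the hazard doubles after loss; in that last scenario the fixed rules themselves gave 0.028-0.029. These figures show what the wording permits. The documents give no ground to infer that a selective search is planned. At the planned HR of 0.4 the choice scarcely affects power; it matters mainly for a borderline result. The change is worth making because it is cheap, removes the discretion and recovers events.

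**What to change.** In Protocol 13.3, state that lost status ends contact attempts but not the ascertainment of vital status. In 13.4, replace the optional vendor search with one mandatory search:

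- for every randomized subject of unknown status, in both arms, who has not refused and where local law allows;
- on one fixed date before database lock, covering the period through the SAP cut-off;
- by a vendor not told the arm.

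In SAP 7.1.1, count a confirmed death on its date, censor a subject confirmed alive at the cut-off, and keep unresolved subjects censored at last known status as now. Report the numbers searched and resolved by arm, and add a sensitivity analysis without search-derived data.

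The cost is a wording change in both documents and a small vendor fee. At 10% loss about 15 subjects (0.10 × 150) would be searched, through a route the protocol already foresees.

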13.4 RESEARCH DESIGN AND METHODS

While consenting for VTL-308, each subject will be consented to participate in the follow-up VTL-308E protocol as an extension of the protocol. Once consented, they will provide contact information that can be used for 5 years of follow-up (see [Section 5.2.1](#)). This will include a current address and telephone number as well as that of a contact person who may know their whereabouts should they no longer be able to be reached at the phone number or address provided. This contact information (e.g. address, telephone number, contact person) will not be sent to VTL or to their data management contractors. It will be available to study personnel at the investigational site only.

Additionally, subjects will be asked to notify their study Investigator if they are diagnosed with cancer at any time during the 5 years following their VTL-308 participation regardless of when the diagnosis is made in reference to their annual follow-up call. They will be given the contact information necessary to make the notification.

The date of Randomization will be logged on an eCRF. Based on that date, at 6 months, 9 months, 1 year, and then annually for 4 additional years following their date of Randomization, subjects will be contacted by phone by the investigative site. VTL will keep a master log of the coded subjects and their anniversary dates and will send a reminder to the sites within 2 weeks of the time the call should be made. The site will be provided with eCRFs that include the specific questions to ask.

The questions involve the following:

If the subject responds:

When the subject is reached by phone, or if the subject calls the site, he/she will be asked the following:

1. Since your last contact with study staff, have you had a liver transplant?
If yes, obtain the date of the transplant.
2. Since your last contact with study staff, have you been diagnosed with cancer (that is different than any cancer you may have had while in the trial)? If yes, proceed with the following questions:
 - a. What type of cancer were you diagnosed with?
 - b. What was the extent of your metastatic disease (if applicable)? (To be asked as *has your cancer spread? If so, where?*)
3. Have you changed or do you anticipate changing your contact information? If so, please update it now.
4. Have you changed or do you anticipate changing your contact person or their contact information? If so, please update it now.

5. The EQ-5D-5L Quality of Life questionnaire will be completed.

If the call recipient states the subject has expired:

If another person answers and states the subject is deceased, the investigative site's designated caller will ask the following:

6. When did the subject expire?
7. What was the cause of death?
8. Was an autopsy performed? If yes, where can a copy of the report be obtained?
9. Ask if signed approval can be obtained to access the subject's medical records that have the pertinent information (particularly if cancer was present) if the information is not in the medical record at the investigational site. If approval is given, the coordinator will send out the appropriate medical records release form for a legally appropriate family member to sign. A prepaid FedEx return envelope will be included.
10. Was the subject diagnosed with cancer after being in the VTL-308 study? If so:
 - a. What type of cancer was the subject diagnosed with?
 - b. What was the extent of the subject's metastatic disease (if applicable)? Again, ask in terms the caller can understand.
11. Had the subject had a liver transplant? If so, obtain the date of the transplant.

If the subject is deceased, it will be noted on the eCRF and no further follow-up will be initiated. Vital Therapies must be made aware of this to update the call reminder list. Call the office at [contact] and ask for any of the VTL-308 staff. Deaths, incidences of cancer, and liver transplants will not be reported as SAEs, but should be reported to Vital Therapies as soon as feasible.

Subject is not home/available:

If the subject is unavailable, the caller will find out when to call back to speak to the subject, or what a better phone number might be to reach the subject. A call-back number can be left for the subject.

A message can be left on a subject's voicemail or answering machine/service only if it gives no medical information or relationship to the reason of the call. For instance, "This call is for John Doe. Please call Jane at [contact] when you get this message." No reference to a clinic, doctor's office, etc. should be left unless the subject has previously stated this is allowed.

Subject not located or calls not returned:

If a subject is no longer at the number given, continues to be unavailable, or does not return messages for at least 3 attempts, the person listed as the contact person should be notified for information.

If the contact person cannot be reached by phone (at least 3 attempts), a registered letter will be sent to both the study subject and to the contact person requesting contact information for them both.

If no information is forthcoming within 3 weeks of sending the registered letters, the subject will be considered lost to follow-up. No further attempts will be made to reach the subject or the contact person. VTL should be notified of the lost-to-follow-up status by calling the office at [contact] and asking for any of the VTL-308 staff.

If at a later time, the subject or the contact person responds, the study visit should be done at that time, even if it is late. The protocol will resume on the following anniversary, so ensure that VTL is made aware of the late contact to keep the subject on the call reminder list.

The site should look in their medical records for any information regarding possible death of the subject if they get no response to calls. All deaths will be noted on the eCRF.

Prior to calling a subject annually, the previous year's information will be reviewed to assure no subject contact is inadvertently made if the subject has expired and we have been made aware of it.

For subjects lost to follow-up, whether during or after the 91-day parent study, VTL may engage a third party vendor that specializes in identifying survival status (e.g. through a search of public records). In such cases, this vendor will provide documentation of the survival status to study site, who will then enter this new information in the eCRF.

